9. REFERENCES

GlaxoSmithKline Document Number 2016N281575_03 (amendment no.3 – 30-May-2018): A randomized, open-label study to characterize the pharmacokinetics of IH oxytocin (GR121619) compared with IM oxytocin in women in the third stage of labour, and with IV oxytocin in non-pregnant, non-lactating women of childbearing potential.

CONFIDENTIAL

205920

10. APPENDICES**10.1. Appendix 1: Protocol Deviation Management and Definitions for Per Protocol Population**

This section is not applicable as Per Protocol Population is not defined for this study.

CONFIDENTIAL

205920

10.2. Appendix 2: Schedule of Activities**10.2.1. Protocol Defined Schedule of Events : Group 2****10.2.1.1. Time & Events General Overview****Group 2**

Procedure	Study Day		
	Screening ⁵	Main Phase	Follow - Up (7-21 days post dose)
Informed Consent and Demography	X		
Brief Physical Examination	X	X	
Medical history	X		
Pregnancy test	X	X	
Alcohol Breath Test, Smokerlyzer, Urine Drug Screen ¹	X	X	
HIV, Hep B and Hep C screen ²	X		
Inhaler device training / education session	X		
Laboratory assessments (including liver chemistries)	X	X	
Immunogenicity sample		X	X
12-lead ECG	X ⁴	X	
Cardiac Telemetry		X	
Vital signs ³	X	X	
Spirometry (FEV-1) ⁴	X	X	
Admission to unit		X	
Pharmacokinetic blood sample	X	X	
Oxytocin Administration (Ih or Iv)		X	
Prior / concomitant medication review	X	X	X
AE review		----- continuous review -----	
SAE review	----- continuous review -----		
Discharge from unit		X	

1. Smokerlyzer at PI/designee discretion if smoking history in question.
2. If test otherwise performed within 3 months prior to first dose of study treatment, repeat testing at screening is not required.
3. Includes blood pressure, heart rate, temperature, respiratory rate, and SpO2.
4. Performed in triplicate.
5. To be completed within 28 days of randomization.

CONFIDENTIAL

205920

10.2.1.2. Time & Events - Main Phase Procedures

Group 2 - Sessions 1 and 2

Procedure	Pre-dose	Time Post Dose														
		2 min	3 min	5 min	8 min	10 min	15 min	20 min	30 min	45 min	1 hr	1.5 hr	2 hr	2.5 hr	3 hr	4 hr
Brief Physical Exam	X															
Pregnancy Test	X															
Alcohol Breath Test, Smokerlyzer, Urine Drug Screen ¹	X															
Vital signs ²	X			X			X		X		X					X
12-lead ECG	X	X				X		X	X		X					X
Cardiac Telemetry		-----Continuous-----														
Spirometry ³	X											X				
Pharmacokinetic blood sample	X ⁵	X	X	X	X	X	X	X	X	X	X	X	X	X	X	X
Immunogenicity Sample	X															
Laboratory assessments (including liver chemistries)	X															X
Prior medication review	X															
Concomitant medication review		-----continuous review-----														
AE review		-----continuous review-----														
SAE Review		-----continuous review-----														
Discharge from unit ⁴																X

1. Smokerlyzer at Principal Investigator (PI)/designee discretion if smoking history in question.
2. Includes blood pressure, heart rate, temperature, respiratory rate, and SpO2
3. FEV 1.0 will be performed in triplicate at each time point. Record all three values on source document, and record best effort in eCRF.
4. Discharge at PI discretion, no sooner than 4-hours post-dose.
5. 3 pre-dose samples: approximately 1 hr pre-dose, 30 minutes pre-dose, and 15 minutes pre-dose

CONFIDENTIAL

205920

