
 To characterize the pharmacokinetics 	
 Plasma concentration time profile for IH oxytocin and 5

CONFIDENTIAL

205920

Objectives	Endpoints
of single doses of IH oxytocin and 5 I.U. IV oxytocin.	I.U. IV oxytocin. 
 PK parameters: Cmax, Cp10, Cp20, Cp30, tmax, AUC, Plasma clearance (CL), volume of distribution and t1/2 will be calculated as data permit.
Exploratory Objectives	Exploratory Endpoints

 To evaluate endogenous plasma oxytocin concentrations in non-pregnant females in the presence and absence of the combined oral contraceptive. 	
 Pre-dose plasma concentrations of oxytocin.

 To compare the IH pharmacokinetics of oxytocin between Cohort A (subjects on combined oral contraceptive) and Cohort B (subjects using a non-hormonal form of contraception). 	
 Cp10, Cp20, Cp30, Cmax, AUC(0-3h), Area under the concentration time curve from time zero to infinity (AUC[0-∞]) and t1/2, will be compared as data permit.

 To compare the IV pharmacokinetics of oxytocin between Cohort A and Cohort B. 	
 Cmax, AUC, t1/2, CL and Volume of distribution (VOD) will be compared as data permit.

Groups 1 and 2 – Women in TSL and Non-pregnant, non-lactating females of child bearing potential

Objectives	Endpoints
Primary Objectives	Primary Endpoints

 To compare pharmacokinetics of IH oxytocin between Group 1 and Group 2 	
 Cp10, Cp20, Cp30, AUC(0-3h) Cmax, AUC(0-3h) AUC(0-∞), and t1/2 will be compared as data permit.

CONFIDENTIAL

205920

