7.3. Other Safety Analyses

The analyses of non-laboratory safety test results including ECGs and vital signs will be based on GSK Core Data Standards, unless otherwise specified. The details of the planned displays are presented in [Appendix 12: List of Data Displays](#).

CONFIDENTIAL

205920

8. PHARMACOKINETIC ANALYSES : GROUP 2

8.1. Primary Pharmacokinetic Analyses : Group 2

8.1.1. Endpoint / Variables : Group 2

- Plasma concentration time profile for IH oxytocin and 5 I.U. IV oxytocin.
- PK parameters: C_{max}, C_{p10}, C_{p20}, C_{p30}, t_{max}, AUC(including AUC(0-t), AUC(0-inf) and AUC(0-3h)), Plasma clearance (CL), volume of distribution and t_{1/2} will be calculated as data permit

8.1.1.1. Drug Concentration Measures : Group 2

Refer to [Appendix 5: Data Display Standards & Handling Conventions \(Section 10.5.3. Reporting Standards for Pharmacokinetic\)](#)

8.1.1.2. Derived Pharmacokinetic Parameters: Group 2

Pharmacokinetic parameters will be calculated by standard non-compartmental analysis according to current working practices and GSK procedures using the currently supported version of WinNonlin. All calculations of non-compartmental parameters will be based on actual sampling times. Pharmacokinetic parameters listed will be determined from the plasma concentration-time data, as data permits.

Treatment	Parameter	Parameter Description
IH/IV	C _{max}	Maximum observed concentration, determined directly from the concentration-time data.
IH/IV	Pre - dose	Quantified concentration in PK sample collected at predose, determined directly from the concentration-time data.
IH	C _{p10}	Quantified concentration in PK sample collected at 10 minutes (nominal time) post-dose, determined directly from the concentration-time data.
IH	C _{p20}	Quantified concentration in PK sample collected at 20 minutes (nominal time) post-dose, determined directly from the concentration-time data.
IH	C _{p30}	Quantified concentration in PK sample collected at 30 minutes (nominal time) post-dose, determined directly from the concentration-time data.
IH/IV	t _{max}	Time to reach C _{max} , determined directly from the concentration-time data.
IH/IV	AUC(0-t)	Area under the concentration-time curve from time zero to the time of the last quantifiable concentration (C(t)) will be calculated using the linear trapezoidal rule for each incremental trapezoid and the log trapezoidal rule for each decremental trapezoid.

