IH/IV	AUC (0-inf)	Area under the concentration-time curve extrapolated to infinity will be calculated as: $AUC = AUC(0-t) + C(t) / \lambda_{z}$
IH/IV	AUC(0-3h)	Area under the concentration-time curve from time zero to 3 h post-dose
IV	Plasma clearance (CL)	Plasma clearance (a volume per time, i.e. a flow) expresses the overall ability of the body to eliminate a drug by scaling the drug elimination rate (amount per time) by the corresponding plasma concentration level.

CONFIDENTIAL

205920

Treatment	Parameter	Parameter Description
IV	VOD	Volume of distribution of a drug gives information on its distribution in the body. Calculated as $VD = \text{Total amount of drug in the body} / \text{Drug blood plasma concentration}$.
IH/IV	t1/2	Apparent terminal half-life will be calculated as: $t_{1/2} = \ln 2 / \text{Lambda}_z$ (NOTE: Lambda_z is the terminal phase rate constant).
IH/IV	Clast	Last observed quantifiable concentration
IH/IV	tlast	Time of the last observed quantifiable concentration
IH/IV	Lambda_z	The first order rate constant associated with the terminal (log-linear) portion of the concentration-time curve.
IH/IV	Lambda_z_lower	First time point used in computing Lambda_z .
IH/IV	Lambda_z_upper	Last time point used in computing Lambda_z .
IH/IV	#pts	Number of points used in computing Lambda_z .
IH/IV	r-squared	R-squared of Lambda_z computation.
IH/IV	AUC(0-inf)/D	AUC(0-inf) corrected for dose

NOTES:

- Additional parameters may be included as required.

The absolute bioavailability (F) will be derived for each subject using the formula outlined below. If dose normalised AUC(0-∞) cannot be determined this will be substituted with dose normalised AUC(0-t) for that profile. All PK parameters (including the derived inhaled bioavailability, F) will be listed and summarised.

$$F = \frac{AUC(0-\infty)_{inhalad} / Dose_{inhalad}}{AUC(0-\infty)_{IV} / Dose_{IV}}$$

The conversion factor to normalise IV doses is 1 IU = 1.7 mcg oxytocin

8.1.2. Summary Measure: Group 2

Pharmacokinetic data will be presented in graphical and/or tabular form and will be summarized descriptively by IH oxytocin , IV Bolus Oxytocin, IV Infusion Oxytocin for each Cohort (Cohort A and Cohort B). In addition data for the derived absolute bioavailability, F will also be summarised by cohort.

For each of the parameters the following summary statistics will be calculated

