8.3.4.1. Statistical Methodology Specification

Endpoint / Variables

 For IH: - Cp10, Cp20, Cp30, AUC(0-3h), Cmax, Area under the concentration time curve from time zero to infinity (AUC[0-∞]) will be compared as data permit. 
Note: These endpoints will be log transformed for analysis.

Model Specification

 Mixed Effect model will be used to analyze the data. Endpoint: log transformed PK parameter Fixed effect: Cohort (COC/Non-COC) Random effect: Subject The Kenward and Roger method for approximating the denominator degrees of freedom and correcting for bias in the estimated variance-covariance of the fixed effects will be used. An unstructured covariance structure for the G matrix will be used. In the event that this model fails to converge, alternative covariance structures may be considered such as VC or CS. Akaike's Information Criteria (AIC) will be used to assist with the selection of covariance structure.

CONFIDENTIAL

205920

Model Checking & Diagnostics

 • For the Mixed Model, model assumptions will be checked, and appropriate adjustments may be applied based on the data. • Distributional assumptions underlying the model used for analysis will be examined by obtaining a normal probability plot of the residuals and a plot of the residuals versus the fitted values (i.e. checking the normality assumption and constant variance assumption of the model respectively) to gain confidence that the model assumptions are reasonable. • If there are any departures from the distributional assumptions, alternative transformations, such as data squared or square root of data, will be explored. • Non-parametric analyses will be conducted if the normality assumption does not hold.
Model Results Presentation

 • Point estimates and corresponding two-sided 90% confidence intervals for the comparison of interest that is Cohort A (COC) vs Cohort B (non-COC) for IH Oxytocin. These will then be back-transformed to provide point estimates and corresponding 90% confidence intervals for the geometric mean ratios (COC/Non-COC)
Endpoint / Variables

 • $t_{1/2}$, T_{max} Note: This endpoint will not be log transformed for analysis
Model Specification

 • Mann-Whitney test • The test will be performed for IH oxytocin only
Model Results Presentation

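### Group 2 AUC, half-life, clearance, F and the COC versus non-COC comparison rest on total oxytocin, with no baseline-corrected analysis despite three pre-dose samples per session

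*SAP*

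**What the plan says.** All references are to the Group 2 RAP in the SAP unless stated otherwise.

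- **Sampling.** The footnote to the schedule for sessions 1 and 2 (10.2.1.2) specifies "3 pre-dose samples: approximately 1 hr pre-dose, 30 minutes pre-dose, and 15 minutes pre-dose".
- **Objectives.** Section 2.2 has the exploratory objective "To evaluate endogenous plasma oxytocin concentrations in non-pregnant females in the presence and absence of the combined oral contraceptive". The next exploratory objective compares inhaled PK between the same two cohorts.
- **Parameters.** Section 8.1.1.2 defines Cmax as "Maximum observed concentration, determined directly from the concentration-time data", with similar wording for Cp10, Cp20 and Cp30. AUC(0-t) "will be calculated using the linear trapezoidal rule for each incremental trapezoid and the log trapezoidal rule for each decremental trapezoid". AUC(0-3h) is "Area under the concentration-time curve from time zero to 3 h post-dose".
- **Bioavailability.** "The absolute bioavailability (F) will be derived for each subject using the formula outlined below": the ratio of dose-normalised AUC(0-∞), with AUC(0-t) substituted where AUC(0-∞) cannot be determined.
- **Pre-dose value.** It is a parameter of its own, "Quantified concentration in PK sample collected at predose, determined directly from the concentration-time data", and enters no other formula. Section 8.3.2 gives it descriptive statistics.
- **Cohort comparison.** Section 8.3.4.1 lists a single fixed effect, "Fixed effect: Cohort (COC/Non-COC"), a random subject term and no pre-dose covariate. Half-life and tmax are compared by a Mann-Whitney test.

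Neither RAP mentions subtracting or adjusting for a baseline. The nearest rule, in 10.5.2, sets non-quantifiable (NQ) concentrations to zero for summaries. That is imputation, not correction.

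**The concern.** Oxytocin is endogenous, so a measured concentration is the sum of dosed drug and the subject's own level. The plan treats a contraceptive effect on that level as an open question, then compares inhaled PK between the same cohorts on the sum of the two. If the cohorts differ in baseline, the model attributes the difference to inhaled PK and has no term with which to separate them.

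A baseline that persists after the drug has gone also holds up the late concentrations from which lambda_z is estimated. That lengthens t1/2 and inflates the extrapolated part of AUC(0-∞). F is built on AUC(0-∞), and CL, if computed in the usual way as dose over AUC, moves with it.

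The data needed for a correction are already collected, and parameter derivation is set out in full in this document. The choice therefore belongs here.

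**Working it through.** The plan states no figure to reproduce, and no Group 2 endogenous level or expected AUC is given. Everything below is illustration on assumed values. The only numerical inputs from the documents are the sampling times (10.2.1.2, to 4 h) and an assay lower limit of quantification (LLQ) of 2 pg/mL. The LLQ comes from the Group 1 RAP, section 3.1, and is assumed to apply to Group 2.

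**1. Cohort ratio on AUC(0-3h), identical inhaled PK.** A constant baseline B adds 3B to the area, so the ratio is (A + 3·B_COC)/(A + 3·B_nonCOC). With baselines of 4 and 2 pg/mL:

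- A = 30: (30 + 12)/(30 + 6) = 42/36 = 1.17
- A = 60: 72/66 = 1.09
- A = 120: 132/126 = 1.05

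**2. Which parameters move most.** A linear-up/log-down analysis was run on the planned times. Assumptions: noise-free data, one-compartment absorption with absorption half-life 5 min and elimination half-life 15 min, exogenous Cmax 50 pg/mL, values below 2 pg/mL set to zero, and lambda_z from the last three quantifiable points.

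| Baseline (pg/mL) | Cmax | AUC(0-3h) | AUC(0-t) | AUC(0-∞) | t1/2 (h) |
|---|---|---|---|---|---|
| 0 | 50.0 | 31.2 | 30.7 | 31.4 | 0.25 |
| 1 | 51.0 | 33.0 | 32.2 | 33.6 | 0.30 |
| 2 | 52.0 | 37.6 | 39.6 | 93.5 | 18.7 |
| 5 | 55.0 | 46.8 | 51.8 | 382 | 45.8 |

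For the same profile with baselines of 4 versus 2 pg/mL, the apparent cohort ratio is 1.04 for Cmax, 1.16 for AUC(0-3h) and 2.78 for AUC(0-∞). Below the LLQ, at 1 pg/mL, the effect is small.

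**3. F.** On a fixed 3 h window the distortion is [(A_IH + 3B)/(A_IV + 3B)]/(A_IH/A_IV). At B = 2 pg/mL:

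- A_IH 30, A_IV 240: (36/246)/(30/240) = 1.17
- A_IH 60, A_IV 120: (66/126)/(60/120) = 1.05
- equal AUCs: 1.00
- A_IH 120, A_IV 60: (126/66)/(120/60) = 0.95

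The planned F does not use this window. As a rough stand-in for it, pair the Cmax 50 profile above with one of the same shape and Cmax 100; this is not a real IV profile. The true AUC ratio is 0.50.

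- On AUC(0-t), B = 2: 39.63/71.11 = 0.557, a distortion of 0.557/0.50 = 1.11.
- On AUC(0-∞), B = 2: 93.53/98.88 = 0.946, a distortion of 0.946/0.50 = 1.89.

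**4. What a naive correction does at the LLQ.** Suppose cohort baselines are 2.1 and 1.9 pg/mL and exogenous AUC(0-3h) is 30 in both. Uncorrected, the ratio is about (30 + 6.3)/(30 + 5.7) = 36.3/35.7 = 1.02, taking the whole baseline area as counted. If NQ pre-dose is set to zero, the first cohort is corrected to 30.0 and the second is left at up to 35.7, so the ratio can fall to 30.0/35.7 = 0.84. With ½ LLQ (1 pg/mL) for NQ, the second cohort becomes up to 35.7 − 3 = 32.7, and the ratio 30.0/32.7 = 0.92.

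**The case against.** **No evidence of a quantifiable baseline in Group 2.** The only information on levels is in the Group 1 RAP, section 3.1: most samples from women in the third stage of labour were below 2 pg/mL even after dosing. That is a different population, but nothing in the documents supports 2 or 4 pg/mL here. The LLQ is not settled either: the Group 1 mock shell PK_T1 shows ½ LLQ as 5 pg/mL, implying 10, though that may be template text. This stands, and it makes the point conditional.

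**Stakes are limited.** The cohort comparison is exploratory, no formal hypothesis is tested (2.4), and F is not named in the objectives table. A reader would also see the pre-dose summary by cohort beside the ratio. This stands too, although seeing a baseline difference does not tell the reader how much of the ratio it explains.

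**Unseen standards.** The analysis follows sponsor procedures and a guidance document (GUI_51487) that are not shown. The RAP cites that guidance only for imputing concentrations, so it lowers certainty without showing that a correction exists.

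**Correction is not free.** A reader might suppose that subtraction can do no harm, because it changes nothing when pre-dose is NQ. Step 4 shows otherwise: with NQ set to zero, correction switches on at the LLQ and can create a cohort difference larger than the one it removes. The fix has to deal with this.

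**Conclusion.** The plan uses total concentrations throughout and makes no analytic use of pre-dose samples it already takes, while asking in the same section whether the baseline differs between the cohorts being compared. If pre-dose oxytocin is quantifiable, AUC(0-∞) and t1/2 are most exposed, AUC(0-3h) moderately and Cmax least. A cohort difference in baseline would then be read as a difference in inhaled PK.

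The size cannot be derived from the documents. The ratios of 1.17 at an AUC of 30 pg.h/mL and 1.05 at 120 rest on assumed constant baselines of 4 and 2 pg/mL and apply to AUC(0-3h) only.

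Three stronger readings are not supported:

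- That F is biased whenever baseline is quantifiable. On a fixed window the effect vanishes when inhaled and IV AUC are equal, and reverses when the inhaled AUC is larger.
- That the AUC(0-3h) figures in step 3 measure the error in the planned F. F is defined on AUC(0-∞), with AUC(0-t) as substitute, so its distortion could be quite different.
- That Cmax is materially affected. It moves from 50 to 52 pg/mL at a baseline of 2 pg/mL.

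This is a worthwhile, low-cost improvement to an exploratory comparison and a derived parameter, not a flaw that invalidates the analysis.

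**What to change.** In the Group 2 RAP, sections 8.1.1.2 and 8.3.4:

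- Pre-specify a baseline-corrected non-compartmental analysis. For each subject and session, subtract the mean of the three pre-dose values before deriving parameters. State this averaging explicitly: section 10.6.1 averages repeat measurements at one time point, and these samples are at three different times.
- Drop corrected values at or below zero from the log-trapezoid and lambda_z steps.
- Report AUC, t1/2, F and the cohort ratio both corrected and uncorrected.
- Apply one NQ rule to both cohorts, and show the cohort ratio with NQ pre-dose set to 0 and to ½ LLQ. In step 4 the second choice halves the jump at the LLQ but does not remove it, so both results should be shown. State the Group 2 LLQ.

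The cost is one extra non-compartmental run, additional rows in Tables 2.2 to 2.5, and some added noise from estimating the baseline. If all pre-dose values are NQ, the version with NQ set to 0 reproduces the uncorrected results, and the ½ LLQ version shows how far a baseline below the limit could matter.

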10.3. Appendix 3: Assessment Windows

No assessment windows will be applied.

CONFIDENTIAL

205920

10.4. Appendix 4: Study Phases and Treatment Emergent Adverse Events

10.4.1. Study Phases

Assessments and events will be classified according to the time of occurrence relative to study treatment.

Study Phase	Definition
Pre-Treatment	Date ≤ Study Treatment Start Date
On-Treatment	Study Treatment Start Date ≤ Date ≤ Study Treatment Stop Date
Post-Treatment	Date > Study Treatment Stop Date

10.4.1.1. Study Phases for Concomitant Medication

Study Phase	Definition
Prior	If medication end date is not missing and is before 28 days prior to screening visit
Concomitant	Any medication that is not a prior

NOTES:

- Please refer to [Appendix 7: Reporting Standards for Missing Data](#) for handling of missing and partial dates for concomitant medication. Use the rules in this table if concomitant medication date is completely missing.

CONFIDENTIAL

205920

10.4.2. Treatment Emergent Flag for Adverse Events

Flag	Definition
Treatment Emergent	
• Any AE's occurring after Period 1 dosing and before Period 2 dosing (predose), will be considered as Period 1 AE's. Any AE's occurring after Period 2 dosing will be considered as Period 2 AE's.• For studies with greater than one treatment period (e.g., crossover study), if AE onset is during one period and worsens during a later period it would be counted in both periods.

NOTES:

- If the study treatment stop date is missing, then the AE will be considered to be On-Treatment.
- Time of study treatment dosing and start/stop time of AEs should be considered, if collected.

CONFIDENTIAL

205920

10.5. Appendix 5: Data Display Standards & Handling Conventions

10.5.1. Reporting Process

Software	

 The currently supported versions of SAS software 9.4 will be used. 	
Reporting Area	
HARP Server	: UK1SALX00175
HARP Compound	: /arenv/arprod/gr121619/mid205920/final_01
Analysis Datasets	

 Analysis datasets will be created according to Legacy GSK A&R dataset 	
Generation of RTF Files	

 RTF files will be generated for summary tables 	

10.5.2. Reporting Standards

General	

 The current GSK Integrated Data Standards Library (IDSL) will be applied for reporting, unless otherwise stated (IDSL Standards Location: https://spope.gsk.com/sites/IDSLLibrary/SitePages/Home.aspx): 
 4.03 to 4.23: General Principles 5.01 to 5.08: Principles Related to Data Listings 6.01 to 6.11: Principles Related to Summary Tables 7.01 to 7.13: Principles Related to Graphics 	
Formats	

 All data will be reported according to the actual treatment the subject received unless otherwise stated. GSK IDSL Statistical Principles (5.03 & 6.06.3) for decimal places (DP's) will be adopted for reporting of data based on the raw data collected, unless otherwise stated. Numeric data will be reported at the precision collected on the eCRF. The reported precision from non eCRF sources will follow the IDSL statistical principles but may be adjusted to a clinically interpretable number of DP's. 	
Planned and Actual Time	

 Reporting for tables, figures and formal statistical analyses: 
 Planned time relative to dosing will be used in figures, summaries, statistical analyses and calculation of any derived parameters, unless otherwise stated. The impact of any major deviation from the planned assessment times and/or scheduled visit days on the analyses and interpretation of the results will be assessed as appropriate. Reporting for Data Listings: 
 Planned and actual time relative to study drug dosing will be shown in listings (Refer to IDSL Statistical Principle 5.05.1). Unscheduled or unplanned readings will be presented within the subject's listings. 	
Unscheduled Visits	

 Unscheduled visits will not be included in summary tables and/or figures. All unscheduled visits will be included in listings. 	

CONFIDENTIAL

205920

Descriptive Summary Statistics		
Continuous Data	Refer to IDSL Statistical Principle 6.06.1	
Categorical Data	N, n, frequency, %	
Reporting of Pharmacokinetic Concentration Data		
Descriptive Summary Statistics	Refer to IDSL Statistical Principle 6.06.1 Assign zero to NQ values (Refer to GUI_51487 for further details)	
Reporting of Pharmacokinetic Parameters		
Descriptive Summary Statistics. (Loge Transformed)	N, n, geometric mean, 90% CI of geometric mean, standard deviation (SD) of logged data and between geometric coefficient of variation (CVb (%)) will be reported. $CVb (\%) = \sqrt{(\exp(SD^2) - 1) * 100}$ [NOTE: SD = SD of loge transformed data] Following steps can be used to calculate 90% CI for PK parameters: Standard Error = [(Geometric Stdev-1)/Sqrt(N)], Margin of Error = [Standard Error * 1.645], and CI = [Geometric Mean \pm Margin of Error]	
Parameters Not Being Loge Transformed	Tmax, and t1/2	
Summary Tables	The following PK parameters will not be summarised: tlast, Lambda_z, Lambda_z_lower, Lambda_z_upper, #pts and r-squared . The following PK parameters will not be log-transformed: Tmax, t1/2 All other parameters will be summarised as log-transformed and non-log-transformed data as described in Section 8.1.2.	
Listings	Include PK Parameters Cmax, Clast, tmax, tlast, AUC(0-3h), AUC(0-t), AUC (0- ∞), Cp(10), Cp(20), Cp(30) , t1/2, Clearance (IV only), Volume of distribution (IV only), F (Inhaled Bioavailability) Lambda_z, Lambda_z_lower, Lambda_z_upper, #pts and r-squared as data permit	
Reporting of Partial Dose / No treatment		
If in a situation where a subject has received partial dose or a subject has received no treatment in a particular period, then they will be handled as given below:		
	Enrolled, Screened Population	Safety, PK Population
Listings, individual PK figures, Study Population tables without period treatment information	Include	Include
Summary PK figures, Safety and PK tables with treatment information	Include	Exclude
Graphical Displays		
Refer to IDSL Statistical Principals 7.01 to 7.13.		

CONFIDENTIAL

205920

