- **Untransformed Data:** N, n, arithmetic mean, 90% confidence interval (CI) for the arithmetic mean, standard deviation (SD), median, minimum, maximum.
- **Loge-transformed Data:** Geometric mean, 90% CI for the geometric mean, standard deviation (SD) of loge-transformed data and %CVb.

For tmax, and t½ the summary statistics specified for untransformed data above will be

CONFIDENTIAL

205920

generated.

8.1.3. Population of Interest : Group 2

The primary pharmacokinetic analyses will be based on the Pharmacokinetic population, unless otherwise specified.

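### The only formula the Group 2 RAP offers for the 90% CI of a geometric mean adds a unitless term to a mean that carries units, so it does not give a 90% interval

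*SAP*

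**What the plan says.** Section 8.1.2 of the Group 2 RAP lists the log-scale summary for the PK parameters: "Geometric mean, 90% CI for the geometric mean, standard deviation (SD) of loge-transformed data and %CVb". It gives no formula for the interval. Section 10.5.2, in the row for log-transformed PK parameters, repeats the request ("N, n, geometric mean, 90% CI of geometric mean, standard deviation (SD) of logged data") and adds a method introduced by "Following steps can be used to calculate 90% CI for PK parameters". The steps are "Standard Error = [(Geometric Stdev-1)/Sqrt(N)], Margin of Error = [Standard Error * 1.645", and the interval is "CI = [Geometric Mean" plus or minus that margin.

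The same section excludes tmax and t1/2 from log transformation, names a few derivation diagnostics that are not summarised at all, and then says: "All other parameters will be summarised as log-transformed and non-log-transformed data as described in Section 8.1.2". Absolute bioavailability is included, because Section 8.1.1.2 states: "All PK parameters (including the derived inhaled bioavailability, F) will be listed and summarised". The output concerned is Table 2.3, the log-transformed summary by cohort.

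**The concern.** A geometric SD is a multiplicative factor with no unit. Subtracting 1 and dividing by √N leaves a pure number, which is then added to a geometric mean measured in concentration, area, clearance or volume units. Three faults follow.

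- The margin does not scale with the parameter, so the same data give different intervals in different units.
- The interval is symmetric on the raw scale, although the parameter is being summarised on the log scale.
- The multiplier is a normal quantile, although the RAP itself describes the IV bolus and infusion numbers as too small for formal comparison (Sections 2.1 and 2.4). A t quantile is needed there.

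Characterising the PK of inhaled and IV oxytocin is a primary objective of Group 2. For the IV arms, the descriptive summaries are all that is planned. An interval labelled 90% in Table 2.3 that has no stable relation to 90% would misstate the precision of those results.

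**Working it through.** **Inputs from the document.** Two-sided 90% level, multiplier 1.645, and the three steps of Section 10.5.2. The multiplier reproduces: z(0.95) = 1.6449. Doses are 400 mcg inhaled and 5 IU IV, and "The conversion factor to normalise IV doses is 1 IU = 1.7 mcg oxytocin", so IV = 5 × 1.7 = 8.5 mcg.

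**Assumed inputs.** The document gives no cohort size, geometric SD (GSD) or geometric mean (GM). I take N = 10 and GSD = 1.6. By the RAP's own CVb formula this is SD(ln x) = ln 1.6 = 0.470 and CVb = √(exp(0.470²) − 1) = 50%.

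**Recipe.** Margin = 1.645 × (1.6 − 1)/√10 = 0.312, whatever the parameter or unit.

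**Log-scale interval.** t(0.95, 9) = 1.833. The half-width on the log scale is 1.833 × 0.470/√10 = 0.2725, and exp(0.2725) = 1.313. The limits are GM/1.313 and GM × 1.313.

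**Approximate coverage of the recipe when GM is large.** The standard error of mean(ln x) is 0.470/√10 = 0.1486. Coverage is about P(|Z| < 0.312/(GM × 0.1486)). At GM = 50 this is P(|Z| < 0.042) = 3.3%. Simulation of 200,000 lognormal samples gave 32%, 3.3% and 0.3% at GM = 5, 50 and 500.

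| GM | Recipe | Log-scale interval | Recipe width ÷ log-scale width | Recipe coverage |
|---|---|---|---|---|
| 0.02125 | −0.291 to 0.333 | 0.0162 to 0.0279 | 53 | about 100% |
| 5 | 4.69 to 5.31 | 3.81 to 6.57 | 0.23 | 32% |
| 50 | 49.7 to 50.3 | 38.1 to 65.7 | 1/44 | 3% |
| 500 | 499.7 to 500.3 | 380.8 to 656.6 | 1/440 | 0.3% |

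The first row is an illustration for F. If the two routes gave equal exposure, F would be 8.5/400 = 0.02125. The document states no value of F.

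**Unit dependence.** The Group 1 mock shell for AUC(0-t) shows pg.h/mL. The Group 2 statistical-analysis shell (Appendix 13) shows µg.h/mL, a factor of 10⁶. An AUC of 50 pg.h/mL gets 49.7 to 50.3. Written as 0.00005 µg.h/mL, the same AUC gets about −0.312 to 0.312. The log-scale interval is the same in either unit.

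**Sensitivity.** Over N = 5 to 15 and CVb = 30%, 50% and 80% (GSD 1.34, 1.60, 2.02), the margin runs from 0.14 to 0.75. Coverage was simulated at N = 5 and N = 12 with 100,000 samples per cell. The recipe covered 14–19% at GM = 10, 1.4–1.9% at GM = 100 and below 0.2% at GM = 1000. The log-scale interval covered about 90% in every cell. The lower limit turns negative when GM is below the margin: 0.16, 0.29 and 0.49 at N = 12 for the three CVs, and 0.25, 0.44 and 0.75 at N = 5. Only near GM = 1 is the recipe's width close to right (0.89 to 1.30 times the log-scale width), because there a relative error and an absolute error have the same size.

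**Quantile.** Using 1.645 in place of t is a smaller error: t(0.95) is 2.13 at N = 5, 1.83 at N = 10 and 1.80 at N = 12.

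**The case against.** The wording is permissive: the steps are offered as usable. The RAP also defers to the sponsor's display standards, which are not at hand, so the programmed table might use a correct routine. A reader might infer that the RAP mandates the invalid formula; the text does not go that far. What stands is that no other formula for this interval appears in the document, so a programmer who follows the RAP gets wrong limits.

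A second objection concerns reach. The cohort comparison of inhaled oxytocin (Section 8.3.4, Table 2.4) back-transforms 90% limits from a log-scale model and does not use these steps. No hypothesis is tested and no decision rule uses the descriptive interval. The geometric mean, the SD of logs, CVb, the medians and ranges, and the listings are all unaffected, and a reader with the geometric mean, SD of logs and n could rebuild the right limits. All of this stands, and it confines the point to one descriptive column.

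Third, the sizes rest on assumed values. It is tempting to say that F will have a negative limit, or that the intervals are always too narrow. Neither follows. F goes negative only if its geometric mean is below 1.645 × (GSD − 1)/√N, and the direction of the error for the other parameters depends on the reporting unit.

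Finally, a reader might take the N under the square root to be the population count rather than the number with a value. The RAP lists N and n separately but does not define N inside the formula, so this is an ambiguity to remove and not a shown error.

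**Conclusion.** Wrong as written. That the recipe is not a valid 90% interval follows from its algebra and needs no assumption. The size does need assumptions. At N = 10 and GSD = 1.6 the margin is fixed at 0.31, which is 44 times too narrow at a geometric mean of 50. It gives a negative lower limit for any geometric mean below 0.31, which may include F, or AUC if that is reported in µg.h/mL. Other plausible N and GSD move the margin between 0.14 and 0.75 without curing the fault.

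The consequence is limited to the interval column of the log-transformed descriptive summary, Table 2.3. A reader might conclude that the Group 2 PK inference as a whole is unsound. The documents do not support that, because the cohort-ratio intervals are built correctly on the log scale. The Group 1 RAP does not use the formula: its Section 8.1.2 summarises PK parameters by counts, median and range.

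**What to change.** Delete the three steps from Section 10.5.2 of the Group 2 RAP and state for Table 2.3, including F:

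90% CI = exp( mean(ln x) ± t(0.95, n−1) × SD(ln x)/√n ), with n = number of subjects with a non-missing value.

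Do not carry this form to Table 2.2. That table holds untransformed data, including tmax and t1/2, and Section 8.1.2 asks there for a CI of the arithmetic mean: mean ± t(0.95, n−1) × SD/√n.

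The cost is one line of text and one line of code, with no new data. Some printed intervals will become wider; others, such as that for a small F, will become narrower.
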